10.4. STATISTICAL ANALYSIS

CSF biomarker endpoints to be analyzed include: 1) neurogranin, 2) neurofilament light chain, 3) total tau, 4) pTau (T181), 5) A β_{42} , 6) YKL40, 7) IL-6, 8) TNF α , and 9) IL-1 β . Plasma and lymphocyte assays include 1) PTI-125Dx lymphocyte assay, 2) PTI-125Dx plasma assay and 3) mTOR assay. CSF biomarkers may also be measured in plasma. All biomarker data will be analyzed by a two-tailed paired t test or other appropriate statistics.

Although not powered for efficacy, the Cambridge Cognition tests will be analyzed by repeated measures ANOVA or other appropriate statistics.

10.5. SAFETY ANALYSIS

Adverse events reported on case report forms will be mapped to preferred terms and organ systems using the MedDRA mapping system. Vital signs and clinical laboratory results will be descriptively summarized in terms of change from screening values.

10.6. SAMPLE SIZE

Sixty (60) patients will be enrolled in this study. Sample size was determined by estimating the intrasubject variability for log-transformed data from previous studies of new chemical entities (NCEs).

11. STUDY TERMINATION

The study will be terminated following completion of the study or at any time at the discretion of the Sponsor.

12. DATA COLLECTION, RETENTION AND MONITORING

12.1. CASE REPORT FORMS

Electronic case report forms (eCRFs) will be used for each subject. The patients in the study will not be identified by name on any study documents to be collected by the Sponsor (or CRO designee) but will be identified by a unique patient number.

All clinical information requested in this protocol will be recorded in the eCRFs provided by CSI. Case report forms must be completed within 48 hours of a patient's visit. In case of error, the correction will be noted, initialed and dated.

eCRFs must be reviewed and verified for accuracy and signed-off by the Principal Investigator before collection by the Sponsor (or CRO designee). Paper source documents, if used, will remain at the Investigator's site at the completion of the study.

12.2. AVAILABILITY AND RETENTION OF INVESTIGATIONAL RECORDS

The Investigator must make study data accessible to the monitor, other authorized representatives of the Sponsor (or designee) and Regulatory Agency (e.g., FDA) inspectors upon request. To assure accuracy of data collected in the eCRFs, it is mandatory that Sponsor representatives have access to original source documents (e.g., subject records, subject charts, and laboratory reports). During review of these documents, the subject's anonymity will be maintained with adherence to professional standards of confidentiality and applicable laws. A file for each subject must be maintained that includes the signed Informed Consent Form and all source documentation related to that subject. The Investigator must ensure the reliability and availability of source documents for the eCRF.

Investigators are required to maintain all study documentation until notification by CSI that any records may be discarded.

The Investigator is responsible for maintaining adequate case histories in each subject's source records.

12.3. SUBJECT CONFIDENTIALITY

All reports and subject samples will be identified only by the assigned patient number and initials to maintain subject confidentiality. Additional subject confidentiality issues (if applicable) are covered in the Clinical Trial Agreement.

12.4. LIABILITY

In the event of a side effect or injury, appropriate medical care as determined by the Investigator or his/her designated alternate will be provided.

If a bodily injury is sustained, resulting directly from the use of the study drug, the Sponsor will reimburse for reasonable physician fees and medical expenses necessary for treatment of only the bodily injury which is not covered by the subject's medical or hospital insurance, provided that the injury is not due to a negligent or wrongful act or omission by the study doctor and his/her staff. No other compensation of any type will be provided by the Sponsor. Compensation for lost wages, disability or discomfort due to the study is not available.

12.5. ETHICAL AND LEGAL ISSUES

The Investigator and site personnel are responsible for conducting this study in accordance with the ICH, GCP, and all other applicable laws and regulations.

12.5.1. Institutional Review Board

The protocol and Informed Consent Form must be approved by an IRB before the study is initiated. The IRB must comply with U.S. CFR 21 Part 56 and local laws.

Documentation of IRB approval must be provided to the Sponsor. Investigators are responsible for the following:

- Obtaining IRB approval of the protocol, Informed Consent Form, and any advertisements to recruit patients and IRB approval of any protocol amendments and Informed Consent Form revisions before implementing the changes.
- Providing the IRB with any required information before or during the study.
- Submitting progress reports to the IRB, as required, requesting additional review and approval, as needed; and providing copies of all relevant IRB communications to the Sponsor.
- Notifying the IRB within 15 calendar days of all SAEs and unexpected AEs related to study medications reported by the Sponsor to the Investigator.

12.6. INFORMED CONSENT FORM

The Sponsor (or designee) must review the Investigator's proposed Informed Consent Form prior to IRB submission for approval. An IRB-approved copy of the Informed Consent Form will be forwarded to the Sponsor.

The Informed Consent Form documents study-specific information the Investigator provides to the subject and the subject's agreement to participate. The Investigator explains in plain terms the nature of the study along with the aims, methods, anticipated benefits, potential risks, and any discomfort that participation may entail. The Informed Consent Form must be signed and dated before the subject enters the study. The original Informed Consent Form and any amended Informed Consent Form, signed and dated, must be retained in the subject's file at the study site and a copy must be given to the subject.

13. INVESTIGATOR RESPONSIBILITIES

The Investigator agrees to:

- Conduct the study in accordance with the protocol, except to protect the safety, rights, or welfare of patients.
- Personally conduct or supervise the study.
- Ensure that requirements for obtaining informed consent and EC/IRB review and approval comply with ICH, CFR 21 Parts 50 and 56 and local laws.
- Report to the Sponsor any AEs that occur during the study in accordance with ICH, CFR 21 Part 312.64 and local laws.
- Read and understand the Investigator's Brochure including potential risks and side effects of the drug.
- Ensure that all associates, colleagues, and employees assisting in the conduct of the study are informed about their obligations in meeting the above commitments.
- Maintain adequate records in accordance with ICH, 21 CFR Part 312.62, and local laws and have records available for inspection by the Sponsor, FDA, or other authorized agency.
- Ensure that EC/IRB complies with requirements of ICH, 21 CFR Part 56, and local laws and will be responsible for initial and continuing review and approval of the clinical study.
- Promptly report to the EC/IRB and the Sponsor all changes in research activity and unanticipated problems involving risks to patients or others (including amendments and expedited safety reports).
- Comply with all other requirements regarding obligations of Clinical Investigators and all other pertinent requirements listed in ICH, 21 CFR Part 312 and local laws.

15. APPENDIX A – SCHEDULE OF ACTIVITIES

| PROCEDURE | SCREEN 1 (Days -29 to Day -1) | SCREEN 2 (Days -28 to Day 0) | DAY 1 Time=0 | DAY 7 | DAY 14 | DAY 28 |
|--------------------------------------------------------------------|-------------------------------------|------------------------------------|-----------------|----------|-----------|-----------|
| Informed consent | Х | | | | | |
| Medical and medication histories | Х | | X | | | |
| ECG | Х | | Х | | Х | Х |
| Vital signs | Х | | Х | Х | Х | Х |
| Physical examination | Х | | * | * | * | Х |
| FSH Test** | Х | | | | | |
| Biochemistry, hematology, urinalysis | Х | | X | Х | Х | Х |
| MMSE | Х | | | | | Х |
| HCV, HBsAg & HIV screen | Х | | | | | |
| Urine drug screen | Х | | | | | |
| Drug administration | | | Х | Х | Х | Х |
| Blood sample collection for PK analysis | | | | Х | Х | Х |
| Adverse Events | | | Х | Х | Х | Х |
| Blood draw for biomarkers and one time only, APOE genotyping | | | X | | | Х |
| Cambridge Cognition testing | | Х | X | | | Х |
| C-SSRS | Х | | | | | Х |
| CSF draw | | Х | | | | Х |

* Listen to heart and lungs ** If female and last natural menses < 24 months or uncertain

CRO	Contract Research Organization		
CS	Compound Symmetry		
CSF	Cerebrospinal Fluid		
CSI	Cassava Sciences, Inc.		
CSR	Clinical Study Report		
C-SSRS	Columbia-Suicide Severity Rating Scale		
CSV	Comma-Separated Values		
ECG	Electrocardiogram		
eCRF	Electronic Case Report Form		
Emax	The maximum response attributable to the drug		
EOD	End of Drug		
EOS	End of Study		
FAS	Full Analysis Set		
FDA	Federal Drug Association		
FSH	Follicle Stimulating Hormone		
GCP	Good Clinical Practice		
IE	Inclusion/Exclusion Criteria		
Kg	Kilogram(s)		
LS	Least Squares		
MedDRA	Medical Dictionary for Regulatory Activities		
Mg	Milligram(s)		
mg/DI	Milligrams per deciliter		

Statistical Analysis Plan

M	Milliliter(s)
Mm	Millimeter(s)
MMSE	Mini-Mental State Examination
MmHg	Millimeters of mercury
PK	Pharmacokinetics
RTF	Rich Text Format
SAE	Serious Adverse Event
SAP	Statistical Analysis Plan
SAS	Statistical Analysis Systems
SD	Standard Deviation
SE	Standard Error
SI	International System of Units
SOC	System and Organ Class
SP	Safety Population
TEAE	Treatment-emergent AE
TLF	Tables, Listings, and Figures
VS	Vital Signs
VC	Variance Component
WHO-DD	World Health Organization Drug Dictionary

Live v1.2 12Feb2020

Introduction

Purpose

The purpose of this Statistical Analysis Plan (SAP) is to provide a thorough description of statistical methods and presentation of the study data to be used for the analysis of data generated from the clinical trial description in protocol Version dated June 28, 2019 : "A Phase 2b, Randomized, Double-blind, Placebo-controlled, Multiple Dose, Biomarker and Safety Study of PTI-125 in Mild-to-Moderate Alzheimer's Disease Patients". Results from the analyses completed will be included in the final clinical study report for PTI-125-02, and may also be utilized for regulatory submissions, manuscripts, or other clinical development activities.

Post-hoc exploratory analyses not identified in this SAP may be performed at the request of the Sponsor, should further examination of study data be required. These analyses will be clearly identified, where appropriate, in the final clinical study report.

This SAP includes details of data handling procedures and statistical methodology. The final statistical analysis will proceed in accordance with this SAP as approved by both Cassava Sciences, Inc. and Axiom Real-Time Metrics. Any deviation from this SAP will be documented in the final Clinical Study Report (CSR). Any deviations from methods described in the protocol are also detailed and explained in this SAP.

The SAP will be finalized and approved prior to unblinding of any study data. Statistical programming of study data will be initiated as study data accumulates to ensure analysis program are setup and readily available prior to statistical delivery. Arbitrary treatment group assignments must be randomly linked to subjects, effectively rendering any output of programs meaningless.

For the reasons stated here the conduct of the study in the field is considered to be independent of any study outcome that might materialize upon enactment of the currently proposed statistical plan.

1. Study Objectives/Hypothesis Testing

1.1 Study Objectives

Live v1.2 12Feb2020

The primary objectives for this study are to:

- Assess the safety of PTI-125 following 1-month, repeat-dose oral administration in mild-to-moderate Alzheimer's Disease (AD) patients, 50-85 years of age, with 16 ≤ MMSE ≤ 26.
- Assess the effect on biomarkers of PTI-125 following 1-month, repeat-dose oral administration in mild-tomoderate AD patients, 50-85 years of age, with 16 ≤ MMSE ≤ 26.
- Assess the effect on cognition of PTI-125 following 1-month, repeat-dose oral administration in mild-tomoderate AD patients, 50-85 years of age, with 16 ≤ MMSE ≤ 26.

The second objective is to replicate the effects on biomarker shown in the previous open label 1-month study.

The third objective is to investigate a dose response of PTI-125.

1.2 Study Endpoints

1.2.1 Primary Endpoint

The primary endpoint for this study will be to evaluate the change in value of specific cerebral spinal fluid (CSF) biomarkers from the second screening to Day 28 between each dose group and placebo.

1.2.2 Secondary Endpoint

- The secondary endpoint for this study will be to evaluate the change in CSF biomarkers from the second screening to Day 28 within the study treatment groups.
- The secondary endpoint for this study will be to evaluate the change in Cambridge Cognition testing from the Day 1 to Day 28 between each dose group and placebo
- ٩
- The secondary endpoint for this study will be the dose-response of the study drug.

1.2.4 PK Endpoint

The PK endpoint for this study is the C_{min} value from the blood samples taken on Days 7, 14 and 28. CSF to plasma ratio will be determined using the Day 28 CSF and plasma samples.

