4. SUMMARY OF STUDY DESIGN

This is a Phase 2b, multi-center, randomized, double-blind, placebo-controlled, study of PTI-125 in mild-to-moderate AD patients, 50-85 years of age. Approximately sixty (60) patients will be enrolled into the study and randomized to one of three cohorts. Cohorts will receive placebo or PTI-125 at 50 or 100 mg b.i.d. (n=20 per group). Placebo or PTI-125 will be administered as coated tablets.

There will be two screening visits within 30 days of start of the study. Patients meeting initial screening criteria, including a Mini-Mental State Examination (MMSE) score ≥ 16 and ≤ 26 will return for a CSF draw at a second screening visit to confirm that the A β /tau Index is indicative of AD (final inclusion criterion). This CSF sample will also serve as baseline measurement for the YKL40 neuroinflammation and other potential CSF biomarker assays. Cambridge Cognition testing will be conducted at the second screening visit, Day 1, and at the end of the study. Patients will be assessed for suicidality via the Columbia Suicide Severity Scale (C-SSRS) during the first and last visits.

Patients will report to clinic the morning of Day 1. The following will be conducted prior to dosing: Cambridge Cognition testing, a full physical exam, an ECG and a blood draw for clinical labs and biomarkers (PTI-125Dx and mTOR). After dosing, patients will be monitored for adverse events and vital signs will be taken through 4 h. Patients will return to the clinic on Days 7, 14 and 28.

PK blood samples will be obtained prior to the first dose on Day 14 for C_{min} values. On Day 28, there will be a CSF draw after the last dose, and an additional PK blood sample will be obtained after this CSF draw for calculation of CSF/plasma ratio.

Blood draws for clinical laboratory testing will be performed at screening and on Days 1, 7, 14 and 28. Safety assessments of vital signs and listening to heart and lungs will be conducted at all visits. ECGs will be conducted on Days 7, 14 and 28.

Blood samples for testing in PTI-125Dx, the companion diagnostic/biomarker, mTOR activation and other potential blood-based biomarkers will be drawn on Day 1 and Day 28. The Day 28 blood sample will also be used for APOE genotyping. A CSF sample collection will be performed on Day 28 for neurogranin, neurofilament light chain, total tau, pTau (T181), A β_{42} , A β_{40} , YKL40, IL-6, IL-1 β , TNF α and other potential CSF biomarker assays as well as bioanalysis of PTI-125.

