2.0 Background

2.1 Study Design

This Phase 2b study is a randomized, double-blind, placebo-controlled trial of PTI-125 oral tablets given to patients with mild to moderate Alzheimer's Disease. Sixty patients are expected to be enrolled in the trial and randomized to one of the three cohorts. Cohorts will receive placebo or PTI-125 at 50 or 100 mg twice a day.

Two screening visits will be scheduled within 30 days of start of the study (Figure 1) Subjects meeting the initial screening criteria will return for a cerebrospinal fluid (CSF) draw at a second screening visit. A second CSF sample will be collected at day 28 visit for CSF biomarkers as well as analysis of PTI-125. Cambridge Cognition testing will be conducted at the second Screening visit, Day 1 and at the Day 28 visit.

On Screening visit 1 and Day 28, patients will be assessed for suicidality via the C-SSRS.

Subjects will report to the clinic on the morning of Day 1 and the following will be conducted: Cambridge Cognition testing, a full physical exam, an ECG and a blood draw for clinical labs and biomarkers. Subjects will be monitored for Adverse Events (AE) and Vital Signs (VS) will be taken through 2 hours post- dosing. Subjects will return to the clinic on Days 7, 14 and 28 for blood draws for clinical laboratory testing, safety assessments of vital signs, ECGs.

PK blood samples will be obtained prior to the first dose on Day 7, Day 14, and Day 28 for C_{min} values. On Day 28, there will be a CSF draw after the last dose, and an additional PK blood sample will be obtained after this CSF draw for calculation of CSF/plasma ratio.

Blood samples for testing in PTI-125Dx, the companion diagnostic/biomarker, mTOR activation and other potential blood-based biomarkers will be drawn on Day 1 and Day 28. The Day 14 blood sample will also be used for APOE genotyping. A CSF sample collection will be performed on Day 28 for neurogranin, neurofilament light chain, total tau, pTau (T181), A β 42, A β 40, YKL40, IL-6, IL-1 β , TNF α and other potential CSF biomarker assays as well as bioanalysis of PTI-125.

Figure 1. Study Design Schema

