2.7 Schedule of Time and Events

Approximately sixty (60) subjects will be enrolled into the study and randomized to one of three cohorts [(Placebo or PTI-125 at 50 or 100 mg b.i.d. (n=20 per group)].

There will be two screening visits within 30 days of start of the study. Subjects that meet the randomization criteria will return to the clinic for subsequent visits at Days 1, 7, 14 and 28.

The schedule for assessments and timing of events is presented in Table 1

PROCEDURE	SCREEN 1 (Days -29 to Day -1)	SCREEN 2 (Days -28 to Day 0)	DAY 1 Time=0	DAY 7	DAY 14	DAY 28
Informed consent	Х	2				
Medical and medication histories	Х		x			
ECG	X		X		Х	Х
Vital signs	X		Х	Х	Х	Х
Physical examination	Х		*	*	*	X
FSH Test**	Х					
Biochemistry, hematology, urinalysis	Х		Х	х	Х	Х
MMSE	Х					X
HCV, HBsAg & HIV screen	Х					
Urine drug screen	Х					
Drug administration			Х	Х	Х	Х
Blood sample collection for PK analysis				х	X	х
Adverse Events		[X	Х	Х	Х
Blood draw for biomarkers and one time only, APOE genotyping			х			х
Cambridge Cognition testing		Х	Х		1	Х
C-SSRS	Х					Х
CSF draw		Х				Х

Table 1. Schedule of Time and Events

* Listen to heart and lungs ** If female and last natural menses < 24 months or uncertain

Page 12 of 22

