6.2.2 Secondary Efficacy Analysis

CSF Biomarkers at Screening Visit 2 and Day 28 will be compared by using the two tailed paired t-test per each treatment group (Placebo, PTI-125 50 mg, and PTI-125 100 mg). The analysis will be performed based on the FAS population. The means, differences between means of Screening Visit 2 and Day 28, a 2 sided 95% CIs for the difference and the p-values from the t-test will be reported in the summary table.

Cambridge Cognition Test

Results will be summarized for subjects by treatment group. The summary and statistical analysis will be conducted using FAS population. The change from baseline on Day 28 will be analyzed by using a General Linear Model for the ANCOVA. The model will include the change from baseline as the dependent variable, the fixed effect of treatments, and baseline Cambridge cognition measurement as covariate. The means, Least Squares (LS) means, a 2 sided 95% confidence intervals (CI) for each LS means, differences between LS means, a 2 sided 95% CIs for each difference and the p-values from model effects will be reported in the summary table.

Dose Response Analysis 6.2.3

Nonlinear Emax model will be used in dose-response analysis. The model has the following form:

$$R_i = E_0 + \frac{D_i^N \times E_{max}}{D_i^N + ED_{50}^N} + \varepsilon_i$$

Where:

i = patient;

 R_i = The value of response for patient i (ex. Defined to be "Change form Baseline in A β_{42} at Day 28" should be repeated for the remaining CSF Biomarkers);

 D_i = Concentration of the drug in the plasma of the patient *i* at Day 28;

 E_0 = Basal response, when the concentration of the drug is zero or minimal;

 E_{max} = The maximum response attributable to the drug;

ED₅₀ = The concentration that produces half of maximum response;

N = The slope measures the change in response by moving from one concentration level to another;

 ε_i = The random error term for patient *i* – i.i.d and follows normal distribution with mean – 0 and variance.

Treatment group response will be predicted by applying the Emax model which intrinsically has 4 parameters to estimate (E0, Emax, ED50, N). This can be performed with "Proc NLIN" procedure in SAS by arbitrary specifying starting estimates for these parameters by treatment groups.

To assure optimal convergence of the procedure, the following starting estimates will be applied:

	Placebo	PTI-125 50mg	PTI-125 100mg
E ₀	0	Minimum response from observed data	Minimum response from observed data

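### The SAP counts Day 28 as a trough (Cmin) day, but the supplied protocol schedules only a post-dose PK sample on that day

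*SAP*

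**What the plan says.** SAP 1.2.4 takes the Cmin "value from the blood samples taken on Days 7, 14 and 28". SAP 2.1 gives the timing: "PK blood samples will be obtained prior to the first dose on Day 7, Day 14, and Day 28" for Cmin, and on Day 28 "an additional PK blood sample will be obtained after this CSF draw for calculation of CSF/plasma ratio". Read together, these describe two Day 28 plasma samples, one before the dose and one after the CSF draw.

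The supplied protocol describes one. Its Day 7 and Day 14 visits (7.2.4, 7.2.5) each open with a block of assessments in the 30 minutes before dosing, and that block contains the Cmin sample. The Day 28 visit (7.2.6) has no such block. Protocol 10.3 gives a closed list of PK measures: Cmin from pre-dose samples on Days 7 and 14, and the Day 28 sample taken after the CSF draw. Protocol 4 is narrower still for Cmin: "PK blood samples will be obtained prior to the first dose on Day 14".

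In SAP 6.2.3 the Emax regressor is "Concentration of the drug in the plasma of the patient" at Day 28, and ED50 is "The concentration that produces half of maximum response". The section does not say which Day 28 sample is meant. The SAP's Purpose section states: "Any deviations from methods described in the protocol are also detailed and explained in this SAP". It contains no note on the Day 28 PK sample.

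**The concern.** A Cmin is a pre-dose value. If the SAP's endpoint is applied to the sampling in the supplied protocol, Day 28 has nothing that qualifies. A programmer then has two options: leave the Day 28 Cmin blank, or fill it with the only Day 28 concentration available, which is post-dose and expected to lie above trough. The second option would place unlike quantities under one label across Days 7, 14 and 28, and could look like a rise in trough levels late in treatment.

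The SAP has no rule to prevent this. Section 4.3.8 names the software for Cmin but does not tie the label to the time of the sample relative to the dose. The same gap reaches the dose-response analysis, because the SAP describes two Day 28 samples and the Emax model does not name one.

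**Working it through.** No figure in the plan needs reproducing. The check sets the sampling texts side by side.

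| Source | Pre-dose PK days | Day 28 PK samples |
|---|---|---|
| SAP 1.2.4 | Cmin on 7, 14, 28 (timing not stated) | not separated |
| SAP 2.1 | 7, 14, 28 | 2 (pre-dose; after CSF) |
| Protocol 4 | 14 | 1 (after CSF) |
| Protocol 7.2.4-7.2.6 | 7, 14 | 1 (post-dose, after CSF) |
| Protocol 10.3 | 7, 14 | 1 (after CSF) |
| Protocol Appendix A and SAP Table 1 | one untimed mark each on 7, 14, 28 | one mark |

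**Timing on Day 28 (Protocol 7.2.6).** The dose is taken on arrival. CSF is drawn 1-2 h after the dose, once cognitive testing is finished. PK blood follows as soon as possible, with its time after dosing recorded. The sample is therefore drawn at least 1 h after the dose, against 0-30 min before the dose on Days 7 and 14.

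**Where the texts part.** In Protocol 4 the word for the extra post-CSF sample makes it additional to Day 14. SAP 2.1 closely follows that paragraph but adds Days 7 and 28 to the pre-dose sentence, which turns the post-CSF sample into a second one on Day 28.

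**The schedules.** The row "Blood sample collection for PK analysis" carries a single Day 28 mark with no time relative to dose, so it settles nothing.

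**Size.**
- SAP Cmin days with a protocol-scheduled pre-dose sample: 2 of 3.
- PK draws per patient: 1 + 1 + 1 = 3 under the protocol; 1 + 1 + 2 = 4 under SAP 2.1.
- Planned active patients: 20 + 20 = 40. Protocol 7.3.3 has only one sample analysed per placebo patient, so placebo does not add to the Cmin data at stake.
- Active-arm plasma samples, with no dropout: 40 × 3 = 120 under the protocol and 40 × 4 = 160 under SAP 2.1. The difference is 40, all of them Day 28 pre-dose.

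**Direction and amount.** Protocol 7.3.3 says the placebo sample analysed will be from a time close to Cmax. Day 28 is the only scheduled post-dose PK sample, so if that sentence describes this trial's sampling, the protocol itself places Day 28 nearer the peak than the trough. The amount cannot be derived: the documents give human Cmax and AUC from the earlier study, but no human trough, half-life or Tmax.

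**The case against.** The strongest reply is that the loose wording starts in the protocol. The sentence in Protocol 10.3 can be read as grouping the Day 28 sample with the Cmin values, and SAP 1.2.4 may simply condense it. This stands as an explanation of where the SAP wording came from. It does not make the sample a trough, because the same sentence places it after the CSF draw. Nor does it explain SAP 2.1, which states a pre-dose Day 28 draw outright.

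A second reply is that a pre-dose draw was possible. Protocol 7.2.3 tells patients to attend follow-up visits undosed, and SAP 4.3.2 has them attend on Day 28 before the morning dose. That shows feasibility, not a scheduled sample.

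A third is that the SAP cites a protocol version dated June 28, 2019, while the supplied protocol shows no date. If the versions differ, there may be no unexplained deviation. This stands as a limit.

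A fourth is that little hangs on it: SAP sections 6 and 7 contain no analysis of Cmin, and the table shells are in a separate document. This stands and keeps the point modest.

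A reader might also infer more than the texts support:
- *That Day 28 Cmin data are probably missing, or probably mislabelled.* Nothing in the documents ranks one outcome above the other.
- *That ED50 is ambiguous in the data.* That requires two Day 28 samples. Under the supplied protocol only the post-CSF sample exists, so the ambiguity is in the SAP text alone.
- *That 60 samples are lost.* The extra draws appear only in the SAP, so no protocol-scheduled sample is lost. Counting all 60 patients also ignores the single analysed sample per placebo patient.

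**Conclusion.** The contradiction holds between the two supplied texts. SAP 1.2.4 and 2.1 make Day 28 a Cmin day with a pre-dose draw; the supplied protocol schedules one Day 28 PK sample, at least 1 h after the dose. One of the three Cmin days is affected, covering the Day 28 values of 40 planned active patients.

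The consequence is confined to the PK endpoint and to the wording of the dose-response regressor. The primary ANCOVA does not use plasma concentrations, and no hypothesis test in the SAP uses Day 28 Cmin. The point should be corrected, but it does not threaten the trial's main comparison.

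The conclusion assumes that the supplied protocol is the version the SAP describes and that sampling followed Protocol 7.2.6. The size of any concentration difference is unknown; only its direction is expected.

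**What to change.** 1. Reconcile SAP 1.2.4 and 2.1 with Protocol 4, 7.2.6 and 10.3, or record the Day 28 pre-dose sample in the SAP as a deviation from the protocol and explain it. Protocol 4 (Day 14 only) and Protocol 10.3 (Days 7 and 14) should be aligned at the same time.
2. Add a rule that a concentration is summarised as Cmin only if its recorded time is before that day's dose. Drop Day 28 from the Cmin endpoint unless a pre-dose Day 28 sample was actually drawn.
3. Report the Day 28 post-CSF concentration separately, with its time since dose, and use it for the CSF/plasma ratio.
4. State in SAP 6.2.3 which Day 28 sample is the regressor. Under the supplied protocol it can only be the post-CSF sample. If two samples exist, the choice is a modelling decision and should be named before unblinding.

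The cost is SAP wording and one time-relative-to-dose rule in the PK dataset. The protocol already requires the post-dose time of the Day 28 sample to be recorded, so no new samples or data items are needed.
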